4.0 Objectives

Phase 1:

Primary Objectives

1. To determine the maximum tolerated dose (MTD) of the combination of lenalidomide and thalidomide and dexamethasone (LTD) in patients with relapsed/refractory multiple myeloma (RRMM).

Secondary Objectives

1. To determine the Overall response rate (ORR)
2. To determine the Time to progression (TTP)
3. To determine the Progression free survival (PFS)
4. To determine the Time to best response

Phase 2:

Primary objective:

1. To determine the overall (CR + VGPR+ PR) response rate of the combination after 4 cycles of therapy.

Secondary Objectives

1. To determine the CR, VGPR
2. To determine the Time to progression (TTP)
3. To determine the Progression free survival (PFS)
4. To determine the Time to best response
5. To assess the safety of the combination of LTD in patients with RRMM.
6. Time to next therapy
7. Symptom measurement - Multiple-symptom assessment tool

5.1 **Selection of Patients**

5.2 **Inclusion Criteria**

1. Understand and voluntarily sign an informed consent form.
2. Age \geq 18 years at the time of signing the informed consent form.
3. Relapsed/refractory MMM with measurable levels of myeloma paraprotein in serum (\geq 0.5 g/dl), urine (\geq 0.2 g excreted in a 24-hour collection sample), or abnormal free light chain (FLC) ratio.
4. Serum Creatinine \leq 2.5 mg/dl
5. Females of childbearing potential (FCBP)[†] must have a negative serum or urine pregnancy test with a sensitivity of at least 50 mIU/mL within 10-14 days prior to and again within 24 hours of starting lenalidomide and must either commit to continued abstinence from heterosexual intercourse or begin TWO acceptable methods of birth control, one highly effective method and one additional affective method AT THE SAME TIME, at least 28 days before she starts taking lenalidomide. FCBP must also agree to ongoing pregnancy testing. Men must agree to use a latex condom during sexual contact with a female of childbearing potential even if they have had a successful vasectomy. All patients must be counseled at a minimum of every 28 days about pregnancy precautions and risks of fetal exposure. See Appendix A: risks of Fetal Exposure, Pregnancy Testing Guidelines and Acceptable Birth Control methods.

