End-of-Study Visit

If you go off study for any reason, you will have an end-of-study visit. This is usually done about 30 days after the last dose of the study drugs. At this visit, the following tests and procedures will be performed:

You will have a physical exam, including measurement of your vital signs and weight.

- Standard myeloma restaging studies including SPEP, UPEP, Free Light Chain measurements (SIFE, UIFE and Bone Marrow biopsy will be done at time of suspected complete remission to document complete remission)
- Clinical laboratory tests: Blood chemistry [sodium, potassium, chloride, CO₂, calcium, magnesium, phosphorus, blood urea nitrogen (BUN), creatinine, glucose, albumin, total protein, alkaline phosphatase, total bilirubin, aspartate transaminase (SGOT/AST), glutamic pyruvic transaminase (SGPT/ALT), lactate dehydrogenase (LDH)
- Hematology: hemoglobin, hematocrit, white blood cell (WBC) count and differential, and platelet count.

Follow-Up

Subjects who discontinue treatment for any reason, will be followed for 30 days. At treatment discontinuation, subjects will undergo a safety assessment approximately 30 days post the last dose of study drug.

Treatment is to be continued and patients will be followed until progression of disease. Patients eligible for and wishing to pursue stem cell transplant will receive at least 2 courses of therapy and will be followed until stem cell transplant, progression of disease, or treatment failure.

Treatment failure will be defined by progression of disease.

Response and progression will be evaluated in this study using the International uniform response criteria for multiple myeloma (Appendix D).

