3. For neurotoxicity for grade 2 toxicity or higher, hold drug until symptoms subside to baseline, grade 1 or less and then Thal may be restarted at 50% of previous dose. If neuropathy develops again with either Thal another 50% reduction can occur after symptoms resolve to 50 mg every day or every other day.
4. For grade 2 constipation Senna will be added to sodium docusate.
5. For somnolence the dose of Thalidomide should be held until symptoms resolve and then will be reduced 50%.

International Myeloma Working Group uniform response criteria:

Response Subcategory	Response criteria
sCR	CR as defined below plus Normal FLC ratio and Absence of clonal cells in bone marrow ^b by immunohistochemistry or immunofluorescence ^c
CR	Negative immunofixation on the serum and urine and Disappearance of any soft tissue plasmacytomas and \leq 5% plasma cells in bone marrow ^b
VGPR	Serum and urine M-protein detectable by immunofixation but not on electrophoresis of 90% or greater reduction in serum M-protein plus urine M-protein level < 100 mg per 24 h
PR	\geq 50% reduction of serum M-protein and reduction in 24-h urinary M-protein by \geq 90% or to < 200 mg per 24h If the serum and urine M-protein are unmeasurable, ^d a \geq 50% decrease in the difference between involved and uninvolved FLC levels is required in place of the M-protein criteria. If serum and urine M-protein are unmeasurable, and serum free light assay is also unmeasurable, \geq 50% reduction in plasma cells is required in place of M-protein, provided baseline bone marrow plasma cell percentage was \geq 30% In addition to the above listed criteria, if present at baseline, a \geq 50% reduction in the size of soft tissue plasmacytomas is also required
SD (not recommended for use as an indicator of response; stability of disease is best described by providing the time to progression estimates)	Not meeting criteria for CR, VGPR, PR or progressive disease

Abbreviations: CR, complete response; FLC, free light chain; PR, partial response; SD, stable disease; sCR, stringent complete response; VGPR, very good partial response.

^a All response categories require two consecutive assessments made at anytime before the institution of any new therapy; all categories also require no known evidence of progressive or new bone lesions if radiographic studies were performed. Radiographic studies are not required to satisfy these response requirements.

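### Of the three response categories in the primary ORR, only PR has a light-chain rule, so some patients enrolled on FLC ratio alone fit VGPR, or more rarely CR, without any change in disease

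*Combined protocol and SAP*

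**What the plan says.** - **Entry.** Section 5.2, item 3, lists three alternatives: serum paraprotein of at least 0.5 g/dl, urine paraprotein of at least 0.2 g in 24 hours, "or abnormal free light chain (FLC) ratio". The third route carries no minimum FLC level and no minimum marrow plasma-cell percentage.
- **Primary endpoint.** Section 4.0, phase 2: "To determine the overall (CR + VGPR+ PR) response rate of the combination after 4 cycles of therapy".
- **Criteria.** Section 6.7: "Response and progression will be evaluated in this study using the International uniform response criteria for multiple myeloma". The table is printed after the dose modification guidelines at the end of the protocol.
- **VGPR row.** First limb: "Serum and urine M-protein detectable by immunofixation but not on electrophoresis". Second limb: "90% or greater reduction in serum M-protein plus urine M-protein level < 100 mg per 24 h". The word printed between them is 'of', read here as 'or'.
- **CR row.** "Negative immunofixation on the serum and urine and Disappearance of any soft tissue plasmacytomas", with marrow plasma cells at or below 5%.
- **PR row.** If serum and urine M-protein are unmeasurable, a fall of at least 50% in the involved-minus-uninvolved FLC difference takes the place of the M-protein criteria.
- **sCR row.** "CR as defined below plus Normal FLC ratio and Absence of clonal cells in bone marrow".
- **Footnotes.** Every response category needs two consecutive assessments. The footnote meant to define measurable disease points to a table whose number is blank.
- **Use of the count.** Section 7.0 stops for low response at 3 or fewer of 12, 7 or fewer of 24, or 11 or fewer of 36.

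**The concern.** A response category should record improvement since baseline. The PR row does so for FLC-only patients. The first VGPR limb and the CR row describe how the patient looks on the day. That is safe when every patient starts with measurable M-protein, because reaching the state then implies a fall. It is not safe once patients can enter below both M-protein thresholds.

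At stake are the primary estimate and the interim rule, which use the same count. The trial is open-label, single-center and without a control arm, so nothing in the design would reveal or offset a false response.

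**Working it through.** **Step 1: the definitions, applied to one patient.** Take a patient with serum M-protein below 0.5 g/dl, urine below 0.2 g/24 h and an abnormal FLC ratio, positive on immunofixation and negative on electrophoresis. Nothing changes on treatment.

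| Rule | Requirement for this patient | Met with no change? |
|---|---|---|
| Inclusion item 3 | abnormal FLC ratio | yes |
| PR | FLC difference falls by at least 50% | no |
| VGPR, first limb | immunofixation positive, electrophoresis negative | yes |
| Confirmation footnote | same finding twice in a row | yes, if the tests are done |
| SD | none of CR, VGPR, PR or progression | no, because VGPR is met |

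The patient fails the shallower category and fits the deeper one. Nothing in the table says that VGPR or CR must first satisfy PR.

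For CR, the patient would instead need "Negative immunofixation on the serum and urine", no plasmacytoma and marrow plasma cells at or below 5%. No eligibility rule excludes this, but three conditions must hold together.

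**Step 2: reproduce the plan's figure.** Let p be the counted response probability. Stopping early means stopping at the look at 12 or 24:

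P(stop) = P(X12 ≤ 3) + Σ over x = 4 to 7 of P(X12 = x) · P(Y12 ≤ 7 − x),

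where X12 and Y12 are independent Binomial(12, p) counts for the first and second dozen patients.

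At p = 0.30 this is 0.4925 + 0.1611 = 0.6536. Section 7.0 gives 0.654 for a true ORR of 0.3 and true toxicity of 0.1; at that toxicity the toxicity rule adds nothing at three decimals. The response boundaries also reproduce from the stated priors: the posterior probability is 0.916 at 3/12, 0.904 at 7/24 and 0.900 at 11/36.

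**Step 3: add false responders.** Let f be the share of enrolled patients who already fit VGPR or CR at screening. The documents give no value for f, so it is an assumption. With a true ORR of 30% in the rest, counted ORR = 0.30(1 − f) + f.

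| f | Counted ORR | Stop at 12 | Stop at 24 | Early futility stop |
|---|---|---|---|---|
| 0% | 30.0% | 0.493 | 0.161 | 0.654 |
| 1.25% | 30.9% | 0.466 | 0.155 | 0.62 |
| 2.5% | 31.8% | 0.439 | 0.148 | 0.59 |
| 5% | 33.5% | 0.388 | 0.133 | 0.52 |
| 10% | 37.0% | 0.295 | 0.099 | 0.39 |
| 20% | 44.0% | 0.150 | 0.040 | 0.19 |

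The rows at 1.25% and 2.5% correspond to an FLC-only share of 5% or 10% of which a quarter qualify. The rows at 5% and above would need every patient in an FLC-only share of that size to qualify, or a larger share of which only some do.

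A single patient can decide the first look: at 12 patients the posterior probability is 0.916 with 3 responses and 0.823 with 4, against a cutoff of 0.90.

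**The case against.** **The appendix is only a transcription.** Section 6.7 names a published standard, and the printed table is visibly incomplete. The full source may restrict VGPR or CR in these patients; that cannot be judged from the documents. But the printed table is what assessors have, and it gives the wrong answer.

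**Immunofixation is not routine on study.** Section 6.7 schedules electrophoresis and FLC each cycle, and immunofixation only when complete remission is suspected. A reader might infer that clean electrophoresis by itself triggers immunofixation; the text does not say so. This stands as a reason why fewer unchanged patients would have two documented assessments. It does not correct the definition.

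**Not every FLC-only patient is affected.** A patient with a small band still visible on electrophoresis does not meet the first VGPR limb. Read strictly, that limb also asks for M-protein in both serum and urine. Both points stand and pull the realistic share down.

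**FLC rules exist elsewhere.** A reader might infer that PR is the only row in the criteria with one. It is not: sCR requires a normal ratio, and progression uses the FLC difference in patients without measurable M-protein. Neither closes the gap, since sCR only upgrades an existing CR and the progression rule does not decide response.

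**A sensible assessor would not score an unchanged patient as VGPR.** Probably so, but the plan gives no rule to rely on.

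**Conclusion.** The response table is wrong as written for patients enrolled on FLC ratio alone. An unchanged patient who is immunofixation-positive and electrophoresis-negative fails PR yet fits VGPR, and so enters the primary ORR. CR shares the fault by a much narrower route.

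The logic needs no assumption beyond reading 'of' as 'or' in the VGPR row. The size does: it rests on the unknown share f, a true ORR of 30% in the other patients, and every patient in f being scored as a responder. Over f from 0 to 20%, the counted ORR runs from 30 to 44% and early futility stopping falls from 0.654 to 0.19; for f up to 2.5%, stopping stays at 0.59 or above.

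A reader might infer that the futility rule is disabled. The documents do not support that: it is weakened by an amount that may be small and is zero if no such patient enrolls.

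**What to change.** Add two rules to the response table and complete one reference:

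1. No response category may be assigned on a criterion already met at screening. Apply this to a whole category or VGPR limb, not to one component, since plasmacytomas, for example, may be absent at baseline.
2. In patients without measurable serum and urine M-protein at baseline, VGPR and CR also require the existing PR light-chain criterion: a fall of at least 50% in the involved-minus-uninvolved FLC difference.
3. Fill in the blank reference for measurable disease, so that it is clear to whom rule 2 applies.

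Rule 2 borrows a threshold already in the table. A new one, such as a 90% FLC fall for VGPR or a normal ratio for CR, has no basis in the documents, and the latter would move part of sCR into CR.

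The cost is a few lines of text. Serum and urine electrophoresis, immunofixation and FLC are already collected at screening (section 6.5), and electrophoresis and FLC each cycle (section 6.7). The downside is that the counted ORR may be slightly lower.

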Reappearance of serum or urine M-protein by immunofixation or electrophoresis

Development of $\geq 5\%$ plasma cells in the bone marrow^c

Appearance of any other sign of progression (i.e., new plasmacytoma, lytic bone lesion, or hypercalcemia see below)

Abbreviations: CR, complete response; DFS, disease-free survival.

^a All relapse categories require two consecutive assessments made at anytime before classification as relapse or disease progression and/or the institution of any new therapy.

^b for progressive disease, serum M-component increases of ≥ 1 gm/dl are sufficient to define relapse if starting M-component is ≥ 5 g/dl.

^c Relapse from CR has the 5% cutoff versus 10% for other categories of relapse.

^d For purposes of calculating time to progression and progression-free survival, CR patients should also be evaluated using criteria listed above for progressive disease.
